8.1.2 ASTX727 (NSC# 820631)

Chemical Name (Cedazuridine): (4*R*)-1-[(2*R*,4*R*,5*R*)-3,3-difluoro-4-hydroxy-5-(hydroxymethyl)oxolan-2-yl]-4-hydroxy-1,3-diazinan-2-one

Chemical Name (Decitabine): 4-amino-1-[(2*R*,4*S*,5*R*)-4-hydroxy-5-(hydroxymethyl)oxolan-2-yl]-1,3,5-triazin-2-(1*H*)-one

Other Names: Cedazuridine and decitabine; INQOVI®

Classification: Cytidine deaminase inhibitor and DNA hypomethylating agent

CAS Registry Number (Cedazuridine): 1141397-80-9

CAS Registry Number (Decitabine): 2353-33-5

Molecular Formula (Cedazuridine): C₉H₁₄F₂N₂O₅ **M.W.:** 268.21 Daltons

Molecular Formula (Decitabine): C₈H₁₂N₄O₄ **M.W.:** 228.21 Daltons

Approximate Solubility of Cedazuridine: Soluble in dimethylsulfoxide, sparingly soluble in water and 50 mM phosphate, slightly soluble in methanol, and insoluble in acetone, and acetonitrile. Not hygroscopic.

Approximate Solubility of Decitabine: Freely soluble in dimethyl sulfoxide, slightly soluble in water, very slightly soluble in methanol. Hygroscopic.

Mode of Action: Decitabine is a cytidine nucleoside analog that inhibits DNA methylation,

thereby causing hypomethylation of DNA and cellular differentiation and/or apoptosis. Cytidine deaminase (CDA) is an enzyme that catalyzes the degradation of cytidine, including the cytidine analog decitabine. High levels of CDA in the gastrointestinal tract and liver degrade decitabine and limit its oral bioavailability. Cedazuridine is a CDA inhibitor. Administration of cedazuridine with decitabine increases systemic exposure of decitabine.

How Supplied: Astex Pharmaceuticals Inc. supplies and PMB distributes, ASTX727 as a red, film-coated, oval, immediate-release, fixed dose combination (FDC) tablet containing the cedazuridine (100 mg) and decitabine (35 mg).

Inactive ingredients consist of lactose, hypromellose, croscarmellose sodium, colloidal silicon dioxide, magnesium stearate, and Opadry II 85F15458 Red. The Opadry is a tablet coating formula that contains titanium dioxide, polyvinyl alcohol, polyethylene glycol, talc, and iron oxide red. Tablets are plain faced on both sides. Future clinical supply may contain a debossed marking of "H35" on each tablet.

ASTX727 is packaged as 5 tablets per bottle. The bottles are white opaque high-density polyethylene (HDPE) with a child resistant closure containing 1 or 2 desiccant canisters for moisture absorption. Bottles have an induction seal.

Storage: Store intact/unopen bottles at 20°C to 25°C (68°F to 77°F); excursions permitted to 15°C to 30°C (59°F to 86°F).

If a storage temperature excursion is identified outside of the permitted excursion 15°C to 30°C (59°F to 86°F), promptly return ASTX727 to 20°C to 25°C (68°F to 77°F) and quarantine the supplies. Provide a detailed report of the excursion (including documentation of temperature monitoring and duration of the excursion) to [contact] for determination of suitability.

Stability: Stability studies are ongoing.

Route and Method of Administration: Oral. Take ASTX727 tablet approximately at the same time on an empty stomach. Do not eat, drink milk or alcohol 2 hours before and 2 hours after taking ASTX727. Clear liquids such as water, black coffee, or tea are allowed. Take whole tablets with 8 oz. (240 mL) of water; do not crush, cut, or chew the tablet.

Missed dose within 12 hours of the scheduled time can be made up. Patient needs to take as soon as possible and resume the next day on schedule. If the patient fails to make up the dose within 12 hours, the dose should be resumed at the scheduled time the next day.

Potential Drug Interactions: Decitabine had no clinically meaningful effect on the pharmacokinetics of cedazuridine. Cedazuridine increased the exposure of decitabine.

Cedazuridine is an inhibitor of cytidine deaminase (CDA) and as such, drugs known to be metabolized by CDA should be avoided during treatment with ASTX727.

CYP450: Cedazuridine is not a substrate of cytochrome P450 (CYP) enzymes. Cedazuridine does not induce CYP1A, CYP2B6, CYP2C9, or CYP3A or inhibit CYP1A, CYP2B6, CYP2C8, CYP2C9, CYP2C19, CYP2D6, CYP2E1, or CYP3A.

Protein Transporters: Cedazuridine is not a substrate of P-glycoprotein (P-gp), MATE1, MATE2-K, OAT1, OAT3, OATP1B1, OATP1B3, OATP2B1, OCT1, or OCT2, and does not inhibit P-gp, BCRP, MATE1, MATE2-K, OAT1, OAT3, OATP1B1, OATP1B3, or OCT2.

Concomitant use of proton pump inhibitor does not have significant impact on decitabine or cedazuridine exposure.

Protein binding: Plasma protein binding of decitabine is negligible (<1%) and for cedazuridine is low (~34% to 38%), therefore interactions due to displacement of more highly protein bound drugs from plasma proteins are not expected.

Patient Care: ASTX727 can cause fetal harm when administered to pregnant women. For that reason, women of childbearing potential must use highly effective contraception during treatment with ASTX727 and for at least 6 months after the last dose. Men with female partners of childbearing potential should be advised to practice highly effective contraceptive measures of birth control and not to father a child while receiving treatment with decitabine and for 3 months after the last dose. Breastfeeding is not allowed during the study and for 2 weeks after the last dose.

8.1.3 Belinostat (PXD-101) (NSC # 726630)

Chemical Name: (E)-N-hydroxy-3-(3-(N-phenylsulfamoyl)phenyl)acrylamide

Other Names: PXD101; Beleodaq®

Classification: Histone deacetylase (HDAC) inhibitor

CAS Registry Number: 414864-00-9; 866323-14-0

Molecular Formula: C₁₅H₁₄N₂O₄S **M.W.:** 318.35

Approximate Solubility: Water 0.14 mg/mL; ethanol >200 mg/mL; polyethylene glycol 400 ~ 1.5 mg/mL; 1,2-propanediol ~ 0.2 mg/mL

Mode of Action: Histone deacetylases (HDACs) are a family of enzymes that regulate chromatin remodeling and gene transcription via the dynamic process of acetylation and deacetylation of core histones. Belinostat is a novel and potent HDAC inhibitor of the hydroxamate class. It alters acetylation levels of histone and non-histone proteins, thus influencing chromatin accessibility and ultimately gene transcription.

How Supplied: Acrotech Biopharma supplies and the Pharmaceutical Management

Branch, CTEP, DCTD, NCI distributes belinostat in single-use 30 mL clear glass vials with coated stoppers and aluminum crimp seals with “flip-off” caps containing 500 mg belinostat For Injection. The sterile yellow lyophilized product also contains 1000 mg arginine, Ph. Eur/USP.

Preparation: Reconstitute the lyophilized product with 9 mL Sterile Water for Injection to yield a final belinostat concentration of 50 mg/mL. Before intravenous administration, further dilute in 250 mL 0.9 % Sodium Chloride Injection.

Storage: Store intact vials of belinostat at controlled room temperature (20-25°C; 68- 77°F); brief excursions permitted (15-30°C; 59-86 °F). Leave intact vials of belinostat in the secondary packaging until use.

If a storage temperature excursion is identified, promptly return belinostat to controlled room temperature and quarantine the supplies. Provide a detailed report of the excursion (including documentation of temperature monitoring and duration of the excursion) to [contact] for determination of suitability.

Stability: Shelf life stability studies of intact vials of belinostat are on-going; once the lyophilized product is reconstituted, the vialed solution is stable for up to 12 hours at ambient temperature (15-25°C).

Once further diluted in 250 mL of 0.9% sodium chloride, belinostat may be stored at ambient temperature (15-25°C) for up to 36 hours, including the infusion time.

Route and Method of Administration: Infuse belinostat intravenously over 30 minutes through a 0.22 micron in-line filter.

Potential Drug Interactions: Belinostat is primarily metabolized by hepatic UGT1A1, and to a lesser extent by CYP2A6, CYP2C9 and CYP3A4 enzymes. Concomitant use of strong inhibitors of UGT1A1 is not allowed. Use caution when co-administering agents which may compete for UGT1A1 metabolism, such as irinotecan. Patients with known UGT1A1 genetic polymorphisms, such as UGT1A1*28, can have reduced UGT1A1 activity and may be at risk for increased belinostat exposure. If subjects with UGT1A1 genetic polymorphisms are not excluded from study participation, reduced doses are warranted.

In vitro studies have shown belinostat and its metabolites are weak to moderate inhibitors of CYP2C8 and moderate to strong inhibitors of CYP2C9; although, studies did not demonstrate effects when co-administered with warfarin. Avoid CYP2C8 and CYP2C9 substrates during belinostat treatment unless deemed medically necessary.

Avoid concomitant medications that may cause Torsade de Pointes.

Availability: Belinostat (PXD101) is an investigational agent supplied to investigators by the Division of Cancer Treatment and Diagnosis (DCTD), NCI.

Belinostat (PXD101) is provided to the NCI under a Collaborative Agreement between Acrotech

Biopharma and the DCTD, NCI (see Section 13.5).

8.1.4 Agent Ordering and Agent Accountability

8.1.4.1 NCI-supplied agents may be requested by eligible participating Investigators (or their authorized designee) at each participating institution. The CTEP-assigned protocol number must be used for ordering all CTEP-supplied investigational agents. The eligible participating investigators at each participating institution must be registered with CTEP, DCTD through an annual submission of FDA Form 1572 (Statement of Investigator), NCI Biosketch, Agent Shipment Form, and Financial Disclosure Form (FDF). If there are several participating investigators at one institution, CTEP-supplied investigational agents for the study should be ordered under the name of one lead participating investigator at that institution.

Confirmation of patient enrollment is required for initial supply.

Submit agent requests through the PMB AURORA application. Access to AURORA requires the establishment of credentials necessary to access secure NCI Clinical Oncology Research Enterprise (CORE) systems, maintenance of an “active” account status, a “current” password, and active person registration status. For questions about drug orders, transfers, returns, or accountability, call or email PMB any time or use the dialog function in AURORA to communicate with PMB staff. Refer to the PMB’s website for specific policies and guidelines related to agent management.

8.1.4.2 Material Safety Data Sheets

The current versions of the material safety data sheets (MSDS or SDS) for PMB-distributed agents will be accessible to site investigators and research staff through the PMB AURORA application. Questions about MSDS access may be directed to the PMB at [contact] or by using the dialog function in AURORA to communicate with PMB staff.

8.1.4.3 Agent Shortages

Specific guidance on how to address agent shortages for patients already enrolled on a clinical study as well as how to manage potential enrollment of new patients is provided at https://ctep.cancer.gov/branches/pmb/drug_shortages.htm.

Treatment plan modifications being made to avoid immediate hazard to patients is permissible under the Department of Health and Human Services (HHS) regulations at 45 CFR 46.103(b)(4)(iii). In accordance with HHS regulations, local investigators must promptly inform the IRB of record of this unanticipated problem and the management plan for the trial.

8.1.4.4 Agent Inventory Records – The investigator, or a responsible party designated by the investigator, must maintain a complete accountability of the receipt, dispensing and

final disposition of all agents received from the PMB using the appropriate NCI Investigational Agent (Drug) Accountability Record (DARF) available on the CTEP forms page. Store and maintain separate NCI Investigational Agent Accountability Records for each agent, strength, formulation and ordering investigator on this protocol.

Product Quality Complaint (PQC): A product quality complaint is defined as any suspicion of a product defect related to a potential quality issue during manufacturing, packaging, release testing, stability monitoring, dose preparation, storage or distribution of the product, or delivery system. Not all PQCs involve a study subject. Lot or batch numbers are of high significance and need to be provided where and when possible. PQC must be reported to the PMB as soon as the PQC is identified. Report PQC to PMB at [contact] or by using the dialog function in AURORA to communicate with PMB staff.

8.1.5 Investigator Brochure Availability

The current versions of the IBs for the agents will be accessible to site investigators and research staff through the PMB AURORA application. Access to AURORA requires the establishment of credentials necessary to access secure NCI Clinical Oncology Research Enterprise (CORE) systems, maintenance of an “active” account status, a “current” password and active person registration status. Questions about IB access may be directed to the PMB IB Coordinator via email.

9. STATISTICAL CONSIDERATIONS

The proposed study is an open-label, single-arm, Simon 2-stage phase 2 clinical trial. Neither

the combination of belinostat and SGI-110 (guadecitabine) nor the combination of belinostat and ASTX727 have been formally evaluated in a phase 1 dose-finding study and therefore a safety lead-in and continuous safety monitoring rule will be applied to monitor for excessive or unexpected toxicity as described in this section.

There is no approved or accepted standard therapy for CS. Chemotherapy is generally ineffective, and no drug has shown clinical efficacy to date. Conventional CS patients are commonly enrolled on clinical trials in the first-line setting. Although chemotherapy is sometimes employed, efficacy is marginal and toxicity is significant. We expect that many sarcoma oncologists would find a chemotherapy control arm problematic, and this would create a barrier to accrual. For these reasons, a single-arm (non-randomized) design is proposed in this rare disease.

With Amendment 5, the study was modified to substitute ASTX727 for SGI-110 (guadecitabine). These are similar agents with the same mechanism of action. At the time of this modification, 6 patients were enrolled and treated with belinostat and SGI-110 (guadecitabine). We will report safety and efficacy endpoints separately for these 6 patients. These 6 patients will be replaced for the purposes of the original study design. The Simon 2-stage design described below will be conducted among patients treated with belinostat and ASTX727. A new safety lead-in will be performed among the first 6 patients treated with belinostat and ASTX727. The continuous toxicity monitoring rule will also apply. The total sample size for the study will increase from 26 patients to 32 patients, accounting for the 6 patients that will be replaced.

9.1 Study Design/Endpoints

9.1.1 Primary Endpoint

The primary endpoint for this phase 2 study is the objective response rate. Noting that chemotherapy is associated with objective response rates of 8-12% in conventional chondrosarcoma (Fox *et al.*, 2012; Italiano *et al.*, 2013), and most clinical trials with targeted agents have shown response rates of 0%, we will consider an objective response rate of 8% as reflecting the activity of chemotherapy and an objective response rate of 28% suggesting promising activity warranting further study. A Simon optimal 2 stage design is employed. The design calls for 26 patients. In stage one, 13 patients will be enrolled. If 2 or more responses are observed, the study will proceed to full accrual. If 5 or more responses are seen among the 26 patients, the study treatment is considered promising for further study. This design has 85% power with alpha of 0.054 to test for a response rate of 8% (null hypothesis) *versus* 28% (alternative hypothesis). The probability of early stopping is 72%.

With Amendment 5, the study was modified to substitute AST727 for SGI-110 (guadecitabine). At that time, 6 patients had been enrolled and initiated study treatment. We will report safety and efficacy separately for these 6 patients. We will report the objective response rate, progression-free survival and safety and tolerability for this group of patients. These 6 patients will be replaced. The Simon optimal 2 stage design described above will be applied to patients receiving the belinostat and ASTX727 combination.

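### Section 9.1.1 gives the primary Simon design a type I error of 0.054; the stated rule has an exact alpha of 0.045

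*Combined protocol and SAP*

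**What the plan says.** Section 9.1.1 (Primary Endpoint) fixes every input to the design.

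- Null rate: "we will consider an objective response rate of 8% as reflecting the activity of chemotherapy".
- Alternative: "an objective response rate of 28% suggesting promising activity warranting further study".
- Design type: "A Simon optimal 2 stage design is employed".
- Size: "The design calls for 26 patients" and "In stage one, 13 patients will be enrolled".
- Stage one rule: "If 2 or more responses are observed, the study will proceed to full accrual".
- Final rule: "If 5 or more responses are seen among the 26 patients, the study treatment is considered promising for further study".

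The operating characteristics follow: "This design has 85% power with alpha of 0.054 to test for a response rate of 8% (null hypothesis"), with 28% as the alternative, and an early-stopping probability of 72%.

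Sections 9 and 9.1.1 carry the same design over to the belinostat plus ASTX727 patients after Amendment 5. The six SGI-110 patients are replaced and do not count towards it. The figures are therefore part of the current text. No other section gives a different alpha or rule for the primary endpoint.

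**The concern.** A two-stage rule with fixed cut-offs has one exact alpha, one exact power and one exact early-stopping probability at given response rates. All three can be checked from Section 9.1.1 alone. Two of them agree with the rule and the third, alpha, does not.

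Alpha is the probability that a regimen no better than the 8% benchmark is called promising, in the only formal test of the primary endpoint. As printed, the test looks slightly above the conventional 5% level when it is below it. The printed value also sits badly with the design's description as optimal: if 0.054 is taken as the limit to which the design was built, the optimum is a different design. Anyone who recalculates the design will find a figure that does not reproduce and cannot tell from the text whether the cut-offs, the null rate or the alpha is the mistake.

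**Working it through.** **Inputs (all from Section 9.1.1).** p0 = 0.08, p1 = 0.28, n1 = 13, N = 26, so n2 = 13. Stop at 0 or 1 responses in stage one. Declare promising at 5 or more in total.

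**Formulas.** With X1 and X2 independent Bin(13, p):

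- Early stopping = P(X1 ≤ 1).
- Probability of declaring promising = sum over x = 2 to 13 of P(X1 = x) × P(X2 ≥ 5 − x).

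Alpha is the second quantity at p = 0.08, and power is the same quantity at p = 0.28.

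**The plan's figures that reproduce.**

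- Early stopping at 8%: P(X1 = 0) + P(X1 = 1) = 0.3383 + 0.3824 = 0.7206 (from unrounded terms). Stated 72%.
- Power at 28%: 0.8512. Stated 85%.

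Because both agree, the cut-offs have been read as the authors meant them.

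**Alpha at 8%.**

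| x in stage one | P(X1 = x) | P(X2 ≥ 5 − x) | Product |
|---|---|---|---|
| 2 | 0.19950 | 0.07987 | 0.01593 |
| 3 | 0.06361 | 0.27937 | 0.01777 |
| 4 | 0.01383 | 0.66175 | 0.00915 |
| 5 | 0.00216 | 1 | 0.00216 |
| 6 | 0.00025 | 1 | 0.00025 |
| 7 or more | 0.00002 | 1 | 0.00002 |

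The sum is 0.0453 (unrounded 0.04529). A simulation of 4 million trials gives 0.0452. The stated value is 0.054.

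**Could another reading give 0.054?**

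- With no interim stop, 5 or more of 26 at 8% has probability 0.0523. A futility stop only removes paths to success: here it removes 0.0008 (x = 0) + 0.0062 (x = 1) = 0.0070, and 0.0523 − 0.0070 = 0.0453. So 0.0523 is a ceiling for any stage one futility rule with this final cut-off, and 0.054 lies above it.
- Changing one element at a time, alpha is: continue at 1 or more, 0.0515; continue at 3 or more, 0.0294; success at 4 or more, 0.1141; success at 6 or more, 0.0139; N = 25, 0.0400; N = 27, 0.0508; N = 28, 0.0565; n1 = 12, 0.0428; n1 = 14, 0.0473. None is 0.054.
- The stated rule reaches 0.054 only at a null rate of about 8.4%.

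**Is it the optimal design, and at which alpha limit?** The Simon optimum minimises the expected sample size under the null, n1 + (1 − early stopping) × n2, subject to limits on alpha and power. With power of at least 0.85:

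- Alpha limit 0.05: n1 = 13, N = 26, cut-offs 2 and 5. Expected size 13 + 0.2794 × 13 = 16.63; alpha 0.0453. This is the protocol's design.
- Alpha limit 0.054: n1 = 12, N = 28, cut-offs 2 and 5. Expected size 12 + 0.2487 × 16 = 15.98; alpha 0.0530; power 0.8538. This is a different design.

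**The case against.** The strongest reply is that nothing in the trial runs on the printed alpha. The decisions at stage one and at the end are response counts, and those are correct, as are the sample size, the power and the early-stopping probability. No p-value for the primary endpoint is compared with 0.054. The true alpha is lower than stated, so the error overstates the risk of a false positive. The protocol sets no 5% limit for this endpoint, and an alpha slightly above 0.05 would not by itself be a defect in a single-arm phase 2 trial. Section 9.1.1 also reports 0.054 as a property of the design, not as the limit used to find it, so the comparison with the 12/28 design is supporting evidence only.

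All of this stands as a comment on consequence. It limits the point to a reporting error with no effect on patients or on the go/no-go decision. Nor is this the only formal test in the protocol: Section 9.4 has a toxicity boundary and Section 9.7 plans tests of correlative endpoints. It is the only formal test of the primary endpoint. None of this makes 0.054 right: as a property of the stated rule, the figure is wrong, and no other section explains or corrects it.

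**Conclusion.** The stated alpha is wrong. Under the rule in Section 9.1.1 the exact one-sided type I error at 8% is 0.0453. The printed 0.054 is 0.054 − 0.0453 = 0.0087 too high, a relative overstatement of 0.0087 / 0.0453 = 19%, and it moves the reported value from below 5% to above it. Power, early stopping, sample size and cut-offs agree with each other and with the description as a Simon optimal design, so the error is confined to this one number.

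The result assumes only independent responses with a common rate and the cut-offs as written. Transposed digits (0.045 printed as 0.054) are a plausible cause, but that is an inference and the conclusion does not depend on it. The correction is certain and its practical effect modest: the design is sound and somewhat stricter than the text says.

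**What to change.** In Section 9.1.1, change the alpha from 0.054 to 0.045 and label it exact and one-sided. Leave the response rates, both cut-offs, the sample size, the 85% power and the 72% early-stopping probability unchanged.

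The cost is one number in the protocol text, which can go into the next amendment. Accrual, conduct, the interim decision and the final decision rule are not affected. Any later report that describes the design should use the corrected figure.

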9.1.2 Secondary Endpoints

Secondary endpoints are the presence of treatment related AEs, the occurrence of DLTs, and PFS. Adverse events will be recorded at each clinical visit and will be categorized according to NCI CTCAE version 5.0. The attribution of AEs to each of the study drugs will also be recorded.

Secondary endpoints will be reported separately for the population of patients receiving belinostat and SGI-110 (guadecitabine) and the population of patients receiving belinostat and ASTX727.

The study will use a continuous toxicity monitoring rule as described in Section 9.4. DLTs are defined in Section 9.2 and to qualify as DLT must be attributed to the study drugs and not to disease, and occur (or first become evident) during the first four cycles of treatment for the purposes of continuous toxicity monitoring.

PFS is defined as the time from first treatment with the study drug to the earliest of either disease progression or death from any cause. Patients who are alive and progression free will be censored at the time of their last follow-up.

